 621 weekly basis and any Serious Adverse Experiences identified will be reported
 622 promptly to the Group Health HSRC and the DSM Body. If an adverse event is
 623 reported by phone, the study staff member will complete an Adverse Events form,
 624 which will be entered into the database and will alert Project Manager [name] and
 625 Co-I [name] of the new AE report. If a Serious Adverse Experience is identified by
 626 phone, it will be reported as outlined below. Adverse experiences that are not
 627 serious will be recorded and included in regular DSM Body reports, but will not be
 628 reported early to the DSM Body. Appendix A details adverse event reporting as
 629 required by the Group Health IRB.

630
 631 Serious Adverse Events that are fatal will be reported to the DSM Body chair within
 632 7 days of discovery, regardless of attribution. The table below details the adverse
 633 event reporting schedule and actions:
 634
 635
 636

| Adverse Event | Action taking by study team (Timeframes for reporting to GH HSRC are described in Appendix A) |
|-----------------------------------|---|
| Serious | |
| Fatal | |
| CBT/MBSR Related ^a | Record on AE and SAE forms Report to DSM Body Chair within 3 days of discovery |
| Not CBT/MBSR Related ^b | Record on AE form Report to DSM Body within 7 days of discovery |
| Not Fatal | |
| CBT/MBSR Related ^a | Report on AE and SAE forms Report to DSM Body within 7 days of discovery |
| Not CBT/MBSR Related ^b | Record on AE form Report to DSM Body as part of regular reports |
| Not Serious | Record on AE form Report to DSM Body and IRB as part of regular reports |

^a possibly, probably or definitely

^b definitely not

638
639
640
641
642
643
644
645
646
647
648
649
650
651
652
653
654
655
656
657
658
659
660
661
662
663
664
665
666
667
668
669
670
671
672
673
674
675
676
677
678
679
680
681
682
683

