| INTERVENTIONS | 
Participants will be randomized to one of three treatments:
 
 • Cognitive Behavioral Therapy (CBT) • Mindfulness-Based Stress Reduction (MBSR) • Usual medical care |
| INTERVENTION SCHEDULE | 8 weekly classes of CBT or MBSR plus daily home practice |
| SAMPLE SIZE | 297 participants (99 CBT, 99 MBSR, 99 usual care) |
| RECRUITMENT PERIOD | Participants will be recruited in 9 cohorts of 33 persons each over a 24-month recruitment period |
| STUDY AIMS | 1) To determine whether Mindfulness-Based Stress Reduction (MBSR) is an effective adjunct to usual medical care for persons with chronic back pain. |

2) To compare the effectiveness of MBSR and group Cognitive-Behavioral Therapy (CBT) in decreasing back pain-related functional limitations and pain bothersomeness.

3) To identify the mediators of any observed effects of MBSR and group CBT on pain-related functional limitations and pain bothersomeness.

4) To compare the cost-effectiveness of MBSR and group CBT as adjuncts to usual care for persons with chronic back pain.

**Co-PRIMARY TRIAL
OUTCOMES**

1) Modified Roland-Morris Disability Questionnaire (back-related dysfunction). This is the most important outcome and was used to calculate statistical power for Aims 1 and 2.

2) Bothersomeness of low back pain (0 to 10 scale).

These outcomes will be measured at baseline, at 4 weeks (during classes), 8 weeks (at the end of classes), 26, and 52 weeks. The 26 week outcomes will be used as the primary endpoint and all other time-points will be considered secondary evaluations.

SAFETY OUTCOMES

Any adverse events identified during classes, on the follow-up interviews or through other means will be documented and reported on a regular basis to the Data Safety Monitoring Body (DSMB). Serious adverse experiences will be reported to the DSMB within 7 days. If attributable to the interventions, serious adverse experiences will also be reported to the IRB within 7 days.

**POTENTIAL MEDIATING
VARIABLES**

We hypothesize: 1) that any benefits of MBSR on participant function and pain bothersomeness will be mediated through increased participant mindfulness and acceptance of pain, and 2) that any benefits of CBT will be mediated through changes in specific cognitions and coping behaviors, as listed in the Specific Aims. We will assess each potential mediator in each follow-up interview.

Mediators of MBSR Effects on Outcomes:

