3.8. Participant Retention and Adherence

A Research Assistant from the study will monitor class attendance in the 8-week CBT and MBSR classes. Participants will receive a reminder call before the first class and whenever they miss any classes. The investigators will use this information to document adherence with these interventions.

During each class, participants will be reminded of the importance of attending classes and of practicing at home. A portion of each class will be devoted to answering questions that arise during home practice and, if necessary, to exploring any perceived barriers to adherence. To monitor adherence with the home practice assigned by the CBT and MBSR instructors we will also ask participants to record their daily home practice on weekly logs. To facilitate accurate reporting of home practice, a study Research Assistant will collect the home practice logs at the beginning of each class. The logs will not be shown to the class instructors. Questions about practice in the prior week will also be included in all follow-up interviews. To maintain interviewer blinding, adherence questions will be asked only after all outcomes data are recorded.

To optimize response rates on the follow-up assessments, we will send advance letters before the all follow-up interviews reminding participants they will be called and we will also compensate them \$20 for their time in completing each of the follow-up interviews. This approach has worked well in our previous studies of yoga, acupuncture, and massage.

418 There are a variety of conceivable reasons participants may prematurely discontinue
419 the class series and study staff will use the following groupings to categorize them:

- 420 - Practice of CBT or MBSR associated with unacceptable or serious adverse
421 experiences from perspective of participant
- 422 - Continued participation considered inadvisable by investigator, class instructor or
423 participant's physician due to concerns that continued participation poses an
424 unacceptable risk to the patient.
- 425 - Participants do not care for the class environment
- 426 - Interventions perceived as ineffective by participant
- 427 - Events in participant's life unrelated to trial (e.g., illness or death in family)

428 A study withdrawal form will be completed for individual who discontinues the
429 intervention. In all cases, participants who discontinue treatments will be encouraged to

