| Exercise in past week (LBP-specific and general) | x | | x | x | x |
| Global improvement (PGIC) | | | x | x | x |
| Program's impact on thoughts, feelings, reactions, activities (open ended) | | | x | x | x |
| EXPLORATORY OUTCOMES: POTENTIAL MEDIATORS | | | | | |
| MBSR: Mindfulness (FFMQ-SF), Pain Acceptance (CPAQ-8) | x | x | x | x | x |
| CBT: Pain beliefs/appraisals (PSEQ; SOPA 2-item Control, Disability, Harm, Emotion scales; PCS), Pain coping strategies (CPCI 2-item relaxation scale, Activity Pacing scale) | x | x | x | x | x |
| EXPLORATORY OUTCOMES: COST-EFFECTIVENESS ANALYSES | | | | | |
| Quality of life (EQ-5D, SF-6D from the SF-12) | x | x | x | x | x |
| Out of plan visits paid for by patients since previous follow-up interview | x | | x | x | x |
| Absenteeism, Presenteeism (WPAI-CLBP) | x | | x | x | x |
| Costs paid by Group Health (payer) for back-related utilization of services (visits, tests, Rx) and total costs. | From electronic medical records for year prior to trial and for follow-up year. | | | | |
| INTERVENTION-RELATED INFORMATION | | | | | |
| Class attendance | | Class Records | | | |
| Adverse experiences from classes or home practice | | X | X | X | X |
| New serious health problems since entering study? | | X | X | X | X |
| Self-reported home practice | | X | X | X | X |
| Perceived helpfulness of classes/home practice | | | X | X | X |
| Would recommend program to friends | | | X | X | X |

510 **Abbreviations:** CPAQ=Chronic Pain Acceptance Questionnaire; CPCI=Chronic Pain Coping Inventory; EQ-5D=European
511 Quality of Life Instrument; FFMQ=Five-Facet Mindfulness Questionnaire; GAD=Generalized Anxiety Disorder scale;
512 GCPS=Graded Chronic Pain Scale; PCS=Pain Catastrophizing Scale; PGIC=Patient Global Impression of Change; PHQ=Patient
513 Health Questionnaire; PSEQ=Patient Self-Efficacy Questionnaire; SF-12=Medical Outcomes Study, Short-Form 12;
514 SOPA=Survey of Pain Attitudes; WPAI-CLBP=Work Productivity and Activity Impairment Questionnaire-Chronic Low Back
515 Pain.

516
517 We will measure a core set of recommended outcomes for spinal disorders (back-
518 related function, pain, general health status, work disability and patient satisfaction) that
519 are consistent with the IMMPACT recommendations for clinical trials of chronic pain
520 treatment efficacy and effectiveness. We will measure outcomes after completion of the

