588 *6.31 Potential Mediators:* For MBSR, we will evaluate the mediating effects of
589 increased mindfulness (measured by the Five Facet Mindfulness Questionnaire) and
590 pain acceptance (measured by the Chronic Pain Acceptance Questionnaire) on the
591 primary outcomes of. For CBT we will evaluate the mediating effects of improvements
592 in pain beliefs/appraisals (measured by the Patient Self-Efficacy Questionnaire; the
593 Survey of Pain Attitudes Control, Disability , Harm, and Emotion Scales; and the Pain
594 Catastrophizing Scale) and improvements in pain coping strategies (measured by the
595 Chronic Pain Coping Inventory’s Relaxation and Activity Pacing scales). Although we
596 expect the effects of MBSR and CBT on outcomes to be mediated by different
597 variables, we will explore the effects of all potential mediators on outcomes for both
598 treatment groups.

599 *6.32. Cost and Effectiveness (Utility) Measures.* Costs will be estimated using cost
600 data from the electronic medical records for back-related services provided or paid by
601 Group Health. The effectiveness of the intervention will be derived from the SF-12
602 general health status measure.

603 604 605 **7. ASSESSMENT OF SAFETY**

606 **7.1 Adverse Events**

607 We will collect data on adverse experiences from several sources and incorporate
608 them into a database. These sources are: 1) reports from the CBT and MBSR
609 instructors of any extraordinary occurrences of concern to them, 2) the computer-
610 assisted telephone-administered 4 and 8, 26 and 52-week follow-up questionnaires
611 will inquire about: any harm they felt from the CBT or MBSR treatments, and any
612 serious health problems, and 3) participants themselves because the consent form
613 directs participants with injuries they believe may be related to the mind-body
614 programs to call the Principal Investigator, Co-Investigators or the Human Subjects

615 Representative, whose names and phone numbers are listed on the copy of the
 616 consent form retained by the participant. Adverse experience data from the
 617 questionnaires will be provided to the Project Manager within a week (and will be
 618 transferred to the AE database). These will be reviewed, as will AE reports from all
 619 sources, by [name], with the assistance of Co-Investigator [name] (a
 620 psychologist) and GHRI physician [name] (a primary care internist) on a

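### No adverse-event source listed in section 7.1 is designed to find deaths or serious events in participants who permanently stop responding, although plan records for the follow-up year are already to be extracted

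*Protocol*

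**What the plan says.** Section 7.1 of the protocol lists where adverse-event data come from: "them into a database. These sources are: 1) reports from the CBT and MBSR" "instructors of any extraordinary occurrences of concern to them"; then the telephone questionnaires at weeks 4, 8, 26 and 52, which "will inquire about: any harm they felt from the CBT or MBSR treatments, and any" serious health problems; then calls from participants with injuries they think the mind-body programs may have caused. The same section requires fatal events to reach the chair of the safety monitoring body within 7 days of discovery whatever their cause. Its table gives 3 days if the death is related to CBT or MBSR.

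Four other places bear on the list:

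- **Section 3.8.** "A study withdrawal form will be completed for individual who discontinues the" intervention. Two of the coded reasons concern safety. One begins "Practice of CBT or MBSR associated with unacceptable or serious adverse" experiences; the other is a judgement by the investigator, instructor or physician that continuing is too risky. No link to the adverse-event form is stated.
- **Section 6, table of measures.** Costs paid by the health plan, both back-related and total, are taken "From electronic medical records for year prior to trial and for follow-up year". Section 12 places the extraction of visit data one year after the last randomization.
- **Protocol Highlights, Safety Outcomes.** "Any adverse events identified during classes, on the follow-up interviews or through other means will be documented".
- **Section 5.** Investigators are in contact with the instructors every week and ask about adverse events, with no threshold of severity.

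**The concern.** Each listed source needs either an instructor or a participant who answers or calls. A participant who dies, becomes too ill to be interviewed or breaks off contact has no dependable route into the database. After the classes end, only the interviews ask about events, and they are 18 weeks apart (weeks 8 to 26) and then 26 weeks apart (weeks 26 to 52).

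Usual Care has no instructor, and the call-in route is worded around injuries from the programs, so in that arm the list comes down to the interviews.

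What is at stake is the completeness of a small count. The reporting clocks in 7.1 start at discovery, so an event that nobody discovers breaks no rule and is simply absent. Section 8 makes the risk of serious adverse events in one or more arms the only ground for stopping, so these counts inform the one decision that the safety data serve.

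**Working it through.** **Number of people concerned.** Inputs from section 9.1: 264 evaluable participants (88 per group), 11% loss, 297 recruited (99 per group).

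- Plan's own figure: 264 / (1 − 0.11) = 296.6, rounded up to 297; 88 / 0.89 = 98.9, rounded up to 99. Both reproduce.
- Planned losses: 297 − 264 = 33, about 11 per arm (297 × 0.11 = 32.67).

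This is an upper figure for permanent silence. Someone who misses one interview can report at the next, because the serious-health question in the section 6 table covers the whole time since entry.

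**Expected events in that group.** The protocol states no serious-event rate, so the risk p is an assumption. Expected events = 32.67 × p. Chance of at least one = 1 − (1 − p)^33.

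| Assumed risk p | Expected events | Chance of at least one |
|---|---|---|
| 0.5% | 0.16 | 15% |
| 1% | 0.33 | 28% |
| 2% | 0.65 | 49% |
| 5% | 1.63 | 82% |

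These are events that no listed source is designed to find. They count as missed only if they also fall after the person's last interview and nobody tells the study.

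**Passages side by side.**

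- *Instructor reports.* Section 7.1 takes what instructors find extraordinary. Section 5 has investigators ask them weekly about adverse events in general. The Highlights promise to document any event identified during classes. The wordings differ in scope, and 7.1 is the narrowest.
- *Stopping classes because of harm.* Section 3.8 codes the reason on a form, and 7.1 does not mention the form. But 3.8 also has participants called when they miss a class, and 7.1 requires an adverse-event form for any event reported by phone. Sections 3.8 and 4 keep people who drop out of classes in the interview schedule. Harm behind a dropout is therefore lost mainly when the person did not mention it by phone and also stops answering.
- *Plan records.* Section 6 commits to follow-up-year records for costs, and total costs require all care, not only back-related care. Section 12 puts the extraction after follow-up. As planned, these records can complete the final count but cannot serve monitoring during the trial.

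**The case against.** The strongest reply is that the safety net is wider than the list in 7.1:

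- Section 5's weekly enquiry and the Highlights' general clause mean that instructor reports are not filtered in practice.
- Section 4 pursues everyone, including those who never attend, drop out, leave the plan or move.
- The serious-health question is cumulative and identical in all arms.
- Consent tells every participant what to do about an adverse event (sections 3.4 and 11.1).
- The protocol describes the interventions as low-risk, and the 11% is a sample-size allowance, not a forecast of permanent silence.

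Most of this stands, and it rules out several stronger conclusions that a reader might infer:

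- *That instructors' reports are cut down to extraordinary events.* Section 5 contradicts this for the protocol as a whole. What remains is a conflict of wording.
- *That harm which caused dropout goes uncounted.* Missed-class calls, the phone-report rule and continued interviews capture most of it.
- *That the trial already holds the follow-up records and could use them for live monitoring.* The health plan holds them; the trial extracts visit data only after follow-up ends.
- *That a known and sizeable share of serious events is missed, or that the arms cannot be compared.* No event rate is given, and all arms get the same question on the same schedule.

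The reply does not reach one point. A promise to document what is identified by other means creates no means of identifying it, and every route just named still depends on someone making contact.

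**Conclusion.** The point holds in a limited form. Section 7.1 has no source designed to find deaths or serious events among participants who permanently stop responding, while the same section makes deaths reportable whatever their cause. The group is at most about 33 of 297 if the planned loss occurs and is permanent. At an assumed risk of 0.5% to 5%, 0.2 to 1.6 events would be expected there, with a 15% to 82% chance of at least one. The count of 33 comes from the protocol; the risks do not.

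The missing link from the withdrawal form and the narrower instructor wording are secondary and mostly a matter of reconciling passages. No sample-size or power figure changes. The gain is a more complete safety count, obtained in the same way in every arm, at low cost.

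**What to change.** In section 7.1:

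1. Add the follow-up-year plan-record extraction, already planned for costs, as a source. Use it to identify deaths, hospital admissions and emergency visits for every randomized participant in all three arms, and include them in the final safety counts by arm. The protocol does not say whether the plan's data carry deaths, so confirm this first. Interim queries before reports to the safety monitoring body can be optional: they would be new surveillance work and are not clearly cheap.
2. State that a withdrawal form marked with either of the two safety reasons in section 3.8 generates an adverse-event form.
3. Reconcile the wording on instructor reports with the weekly enquiry in section 5 and with the Highlights.

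The cost is a little more programming and review, and more unrelated events will be logged. The records give no coverage after a participant leaves the plan, so for those people the interviews remain the main route.

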7.2 Safety Monitoring Body

This is an unmasked Phase II trial comparing CBT, MBSR, and Usual Care for chronic back pain. Given the favorable safety profile from previous studies of CBT and MBSR including our own coupled with the small numbers of adverse events reported in the literature, this trial will be monitored for safety by an independent Data Safety Monitor Body (DSMBody) comprised of a primary care physician experienced in mindfulness, a biostatistician, and a pain psychologist.. The DSMBody’s job will be to evaluate the adverse-experience data we will provide them on a regular basis to protect the safety of the study participants. Based on the observed adverse effects of the treatment under study, the SMB will make recommendations on a regular basis to the PI and the Office of Clinical and Regulatory Affairs at the National Center for Complementary and Alternative Medicine (NCCAM) regarding continuation, termination, or other modifications of the trial.

8. **STOPPING RULES**

The trial will be stopped only if the Safety Monitoring Body (SMB) believes there is an unacceptable risk of serious adverse events in one or more of the treatment arms. In this case, the SMB could decide to terminate one of the arms of the trial or the entire trial. Based on our previous research and on the small number of reports of adverse events from these treatments reported in the literature, we believe the risk of serious adverse events related to our CBT and MBSR interventions is quite small.

9. **STATISTICAL ISSUES**

9.1. Sample Size and the Detectable Difference Our sample was chosen to ensure adequate power to detect a significant difference between each of the two mind-body treatment groups and the Usual Care group, as well as power to detect a difference between the two mind-body treatment groups. Because we consider patient function (or dysfunction) the more consequential of our two primary outcome measures (the other being bothersomeness of back pain), we base our sample size calculations on the modified Roland Disability Questionnaire. We specify our sample size based on the expected percentage of patients with a clinically meaningful improvement on the Roland Score of at least 30% (relative to baseline) at the 26 week follow-up measure.

To protect against multiple comparisons, we will use Fisher’s protected least significance approach, first testing if there is any significant difference among all 3 groups (using the omnibus Chi-Square Likelihood Ratio test). If we find a difference, we will then test for pairwise differences between groups. We will need 264 participants (88 in each group) to achieve 90% power to find either mind-body treatment different from Usual Care. This assumes that 30% of the Usual Care group and 55% of each mind body treatment group will have clinically meaningful improvement at 26 weeks, rates of improvement that are similar to those we observed in a similar back pain population in two studies (one not yet published) evaluating CAM treatments for back pain. Finally, we will have at least 80% power to detect a significant difference between MBSR and CBT if MBSR is at least 21% more effective than CBT (i.e., 76% of the

684 MBSR group versus 55% of the CBT group).

685 Our other co-primary outcome is improvement from baseline on the
686 Bothersomeness Score. With a total sample size of 264 participants, we will have 80%
687 power to find a mind-body treatment group different from Usual Care assuming that
688 47.5% of Usual Care and 69.3% of the mind body treatment groups have 30% or more
689 improvement in the bothersomeness score from baseline.

690 When analyzing the primary outcomes as continuous measures, we will have 90%
691 power to detect a 2.95 point difference in the modified Roland Score and a 1.78 point
692 difference in Bothersomeness score (assumes normal approximation to compare two
693 independent means with equal variances, a two-sided, 0.05 test with standard
694 deviations of 6.0 and 2.4 for Roland and Bothersomeness, respectively (unpublished
695 data from current study of massage for chronic back pain). Thus, we will have ample
696 power for detecting clinically meaningful differences since differences of 2.5 on the
697 Roland scale and 1.5 on the bothersomeness scale are considered clinically
698 meaningful. Assuming 11% loss to follow-up (slightly higher than was found in our
699 previous back pain trials), we plan to recruit a total sample size of 297 participants (99
700 per group).

701 Both co-primary outcomes will be tested at the $p < 0.05$ level at each time point
702 because they address separate scientific questions. Analyses of both outcomes at all
703 follow-up times will be reported, imposing a more stringent requirement than simply
704 reporting a sole significant outcome.

705

706 9.2 Statistical Analysis

707 In our comparisons of treatments on the
708 outcome measures, we will analyze outcomes from all follow-up time points in a single
709 model, adjusting for possible correlation within individuals and treatment group cohorts
710 using generalized estimating equations (GEE). Because we cannot reasonably make
711 an assumption of constant or linear group differences over time, we will include an
712 interaction term between treatment group and time point. We plan to adjust for baseline
713 outcome value, gender, and age as well as other baseline characteristics found to
714 significantly differ by treatment group or follow-up outcomes to improve precision and
715 power. We will conduct the following set of analyses for both the continuous outcome
716 score and the binary outcome clinically significant change from baseline including all
717 follow-up time points (4, 8, 26, and 52 wks). However, since the primary time point is at
718 26 weeks the MBSR treatment will only be deemed successful if the 26 week time point
719 comparisons are significant. The other time points are considered secondary
720 evaluations.

721 We will use an intent-to-treat approach in all
722 analyses; *i.e.*, individuals will be analyzed by randomized group regardless of
723 participation in any classes. This minimizes biases that often occur when participants
724 not receiving assigned treatments are excluded from the analyses. The general form of
725 the regression model will be:

726 $g(Y(t)) = \beta_0 + \beta_1 \text{Baseline} + \alpha_1 \text{Trt} + \alpha_2 \text{Time} + \alpha_3 \text{Trt} \times \text{Time} + \alpha_4 z + \varepsilon$, where $Y(t)$ is the
727 response at follow-up time t , *Baseline* is the pre-randomization value of the outcome
728 measure, *Trt* includes dummy variables for the MBSR and CBT groups, *Time* is a series
729 of dummy variables indicating the follow-up times, and z is a vector of covariates

730 representing other variables being adjusted for. (Note that α_1 , α_2 , α_3 , and α_4 are
731 vectors.) The referent group in this model is the Usual Care group. For binary and
732 continuous outcomes, we will use appropriate link functions (i.e., logit for binary). For
733 each follow-up time point that the omnibus Chi-Square Score test is statistically
734 significant, we will go on to test whether there is a difference between MBSR and Usual
735 Care to address Aim 1 and a difference between MBSR and CBT to address Aim 2. We
736 will also report the comparison of CBT to Usual Care. When determining that MBSR is
737 an effective treatment for back-pain we will require that Aim 1, the comparison of MBSR
738 to Usual Care, must be observed.

739 Based on our previous back pain trials, we
740 expect at least 90% follow-up rate and so our primary analysis will be a complete case
741 analysis including all observed follow-up outcomes, but we will adjust for all baseline
742 covariates that are predictive of outcome, probability of being missing, or differences
743 between treatment groups. By adjusting for these baseline covariates our model
744 assumes that the missing outcome data are missing at random instead of missing
745 completely at random. We will also conduct sensitivity analysis using an imputation
746 method for non-ignorable non-response to evaluate whether our results are robust to
747 different missing data assumptions

748 If MBSR or CBT is effective (relative to usual
749 care and/or each other) in improving either primary outcome at 26 or 52 weeks, we will
750 move to Aim 3 (to identify the mediators of the effects of MBSR and group CBT on pain-
751 related functional limitations and pain bothersomeness). We will perform the series of
752 mediation analyses separately for the two primary outcomes (Roland and pain
753 bothersomeness) and for each separate treatment comparator of interest (usual care-
754 CBT, usual care-MBSR, CBT-MBSR). We will conduct separate mediator analyses for
755 the 26-week and 52-week outcomes (if MBSR or CBT is found effective at those
756 timepoints). Below is the detailed description of the mediator analysis for the 26-week
757 time-point, but a similar analysis will be conducted for the 52-week time-point.

758 We will apply the framework of the widely
759 used approach of Baron and Kenny. Having demonstrated the association between the
760 treatment and the outcome variable (the “total effect” of the treatment on the outcome),
761 the second step will be to demonstrate the association between the treatment and each
762 putative mediator. We will construct a regression model for each mediator with the 4 or
763 8-week score of the mediator as the dependent variable and baseline score of the
764 mediator and treatment indicator as independent variables. We will conduct this for
765 each potential mediator and only include those mediators that have at least a P < 0.10-
766 level significant relationship with the treatment as potential mediators in the following
767 step. The third step is to demonstrate the reduction of the treatment effect on the
768 outcome after removing the effect of the mediator(s). We will construct a multi-mediator
769 inverse probability weighted (IPW) regression model. This approach allows us to
770 estimate the direct effect of treatment after rebalancing the treatment groups with
771 respect to the mediators. The application of the IPW approach, as compared to the
772 traditional approach of adjusting for multiple mediators, allows us to more appropriately
773 account for confounding between a mediator and the outcome both by additional
774 mediators and by other measured variables. Further, we are better able to estimate the
775 indirect effects of each mediator in a causal framework through decomposition of the

776 total effect of treatment into indirect effects through each mediator and the direct effect
777 after accounting for all mediators. Specifically, we will first model the probability of the
778 treatment given the mediators (all mediators that were found associated with treatment
779 in step 2) using logistic regression adjusting for potential baseline confounders. From
780 this model we will obtain the estimated probabilities that each person received their
781 observed treatment given their observed mediator value. We will then use an IPW
782 regression to model the primary outcomes on treatment status while adjusting for the
783 baseline level of the outcome and mediator. Comparing the weighted to the unweighted
784 model will allow us to estimate how much of the direct effect of treatment on the
785 outcome can be explained by each potential mediator. The inclusion in Step 3 of all
786 mediators found to be significant in Step 2 will enable us to examine whether the
787 specific variables we hypothesized to differentially mediate the effects of MBSR versus
788 CBT in fact mediate the effects of each treatment, independently of the effects of the
789 other “process variables”.

790
791 **9.3 Cost Effectiveness Analyses:** A societal perspective cost-utility analysis (CUA) will
792 be performed comparing the incremental societal costs for each treatment arm (direct
793 medical costs paid by GHC and the participant plus productivity costs) to incremental
794 effectiveness in terms of change in QALYs. This CUA can be used by policy makers
795 concerned with the broad allocation of health resources. For the payer perspective,
796 direct medical costs (including intervention costs) will be compared to change in QALYs.
797 This CUA will help determine whether it makes economic sense for MBSR to be a
798 reimbursed service for this population. A bootstrap methodology will be used to estimate
799 confidence intervals. Secondary analyses to assess different cost outcome definitions
800 such as varying assumptions of wage rates used to value productivity and the inclusion
801 of non-back-related utilization in the total cost amounts will also be considered. Cost
802 effectiveness analyses will use intention to treat and will adjust for health care utilization
803 costs in year prior to enrollment and baseline variables that might be associated with
804 treatment group or outcome, such as medication use, to control for potential
805 confounders. We expect minimal missing data, but sensitivity analyses as described for
806 the primary outcomes will also be performed for cost measures.

807
808

809 **10. ORGANIZATION AND ADMINISTRATION**

810 **10.1 Funding and Organizational Oversight**

811 The MAP study is a four-year single-site clinical trial currently funded as a R01 (NIH
812 grant number AT 003208) by the National Center for Complementary and Alternative
813 Medicine (NCCAM). [name], the NCCAM Project Officer assigned to this
814 project, provides NCCAM oversight on the project. A specially-created Safety
815 Monitoring Body will ensure the safety and welfare of patients enrolled in this trial.
816 Budgetary oversight will be provided by NCCAM staff. The study was reviewed and
817 approved by NCCAM’s Office of Clinical and Regulatory Affairs.

818
819

820 **10.2 Organizational Structure**

821 Administrative Leadership is based at the Group Health Research Institute in
822 Seattle. Overall scientific and administrative responsibility for the project resides with
823 [name], the Principal Investigator. [name], Project Manager, is
824 responsible for day-to-day project administration, human resources issues,
825 correspondence with the IRB, supervision of study staff, and coordinating liaison with
826 the CBT and MBSR class instructors. The biostatistician, [name] will have
827 responsibility for ensuring data integrity. The Safety Monitoring Body will have
828 responsible for ensuring the safety of study participants.

829 830 831 10.3 Publications Policies and Procedures

832 The Principal Investigator has responsibility for developing and maintaining a list of
833 proposed publications including topic, names of the primary authors and date proposed.
834 It is the first author's responsibility to determine who will be listed as co-authors and in
835 what order. We will follow the International Committee of Medical Journal Editors'
836 guidelines on authorship on all manuscripts deriving from this study. "Publications" will
837 be a standing item on the agenda for team meetings to ensure open and frequent
838 discussion of this issue. The P.I. will be first author on the primary manuscript, but first
839 authorship on all other manuscripts will be shared.

840 841 **11. ETHICAL PRINCIPLES**

842 **11.1 Informed Consent:** Once a potential participant has been confirmed eligible, a
843 study research specialist will ask the participant if he/she still has the Consent Checklist
844 that was included with the mailed invitation letter. If the participant does not have the
845 Consent Checklist, the Research Specialist will instruct the participant on how to access
846 it on our study website. If the participant does not have internet access, the Research
847 Specialist will mail another copy of the Consent Checklist to the participant, but will
848 continue with the informed consent process. The Research Specialist will guide
849 potential participants through the study consent and HIPAA processes. During the
850 informed consent process, the Research Specialist will explain the study requirements.
851 This will include an explanation of interview time commitments, intervention
852 commitments (coming to 8 class sessions if randomized to CBT or MBSR and home
853 practice expectations), potential risks of participation, potential benefits of participation,
854 what to do for an adverse event, and options for discontinuation of participation in the
855 study. The Research Specialist will also explain the handling of data and personal
856 health information as dictated by HIPAA. Once informed consent has been
857 administered, all questions have been answered, and the potential participant has
858 agreed to take part in the study, the Research Specialist will document the informed
859 consent in the study database. Participants randomized to one of our intervention arms
860 will also be asked to sign a written consent form when they arrive for the first night of
861 class. The Group Health IRB and our DSMB have approved this consenting process for
862 this low-risk intervention and we have obtained a waiver of documentation of written
863 consent from our IRB. All of our Research Specialists have been trained in the process
864 of administering informed consent. The consent checklist contains information about
865 HIPAA as described below.

867 11.2 Health Insurance Portability and Accountability Act (HIPAA)

868 Group Health Cooperative has instituted a protocol that ensures research is
869 conducted in compliance with the federal law entitled, "Health Insurance Portability and
870 Accountability Act (HIPAA)". Permission to use, create, and release personal health
871 information for research will be obtained before potential participants can be enrolled in
872 this study. One of the study Research Specialists will explain HIPAA as it relates to this
873 research study to potential participants to ensure that they understand it and have the
874 opportunity to ask any questions pertaining to their personal health information as it
875 relates to this study. This process will explain what is meant by health information, how
876 health information is obtained, how the researchers may use health information, and
877 detail the steps a participant must take if s/he decides to revoke this permission.
878

879 11.3 Institutional Review Board

880 The investigators are responsible for obtaining initial and continuing review (at
881 intervals of not less than yearly) of the study by their IRB. Written approval from the IRB
882 will be on file prior to commencement of study activities. All key study personnel have
883 Human Subjects Research Training certification on file with the IRB.
884

885 11.4 Confidentiality of Participant Records

886 The investigators and their study teams will maintain strict confidentiality of the
887 participant records. Individual records will be identified by a unique study identification
888 number. Records linking study ID with participant names or other identifying information
889 that may be needed for follow-up interviews, class attendance, etc. will be kept separate
890 from the study data and will be accessed only by study team members on a need-to-
